The adjunctive medication protocol will include scheduled alternating ibuprofen and tylenol unless contraindicated by renal impairment. Both groups of patients will also have oral oxycodone available as needed for moderate breakthrough pain and IV morphine for severe pain. The total dose of local anesthetic for group B will be same as that of group LA.

Primary outcome: We will compare the two groups on their total narcotic dose in milligram morphine equivalents (MME) needed for 48 hours after procedure. This is calculated as intravenous fentanyl (mcg) x0.03+intravenous hydromorphone (mg)x20+intravenous morphine(mg)x3+[number of oral oxycodone 5 mg/acetaminophen 325 mg tabs equivalents]. The 48 hour mark is picked since the local anesthetic duration for either local infiltration or block is 6-12 hours and most patients would be discharged prior to the 48 hour mark. This also allows for sufficient time for complications to develop and tracked as secondary outcomes.

Secondary outcome: VAS pain score in PACU, incidence of pruritus, nausea/vomiting, respiratory depression, local anesthetic toxicity and pneumothorax, these complications would arise early in the post procedure period but would be tracked for 48 hours.

Statistical Analysis

Data will be analyzed within one month after completion of data collection for all enrolled patients. The de-identified data will be uploaded to PI's UTH-Share account and shared with the statistician. We will report the summary statistics of demographics and disease-related characteristics for two groups. The primary endpoint, amount of morphine equivalent administered intra-operative and during the first 24 hours after procedure, will be summarized as median and inter-quartile, and depicted as side-by-side boxplot. Comparison between two groups will be evaluated by Wilcoxon rank sum test. We will report the incidence rates of side effects including pruritis and nausea, as

well as complications including local anesthetic toxicity and pneumothorax. The Wald test will be used for comparing incidence rates between two groups.

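### The primary-endpoint formula counts 100 mcg of IV fentanyl as 1 mg of IV morphine, which under-weights fentanyl about 5- to 10-fold if it is 50 to 100 times as potent by weight

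*Combined protocol and SAP*

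**What the plan says.** The Primary outcome paragraph compares the groups on "total narcotic dose in milligram morphine equivalents (MME) needed for 48 hours after procedure". It computes this as "intravenous fentanyl (mcg) x0.03+intravenous hydromorphone (mg)x20+intravenous morphine(mg)x3", and adds "number of oral oxycodone 5 mg/acetaminophen 325 mg tabs equivalents" with no multiplier printed. This is the only definition of the score. No equianalgesic table or other source is cited for any weight, and no expected opioid doses are given.

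The Statistical Analysis section describes the primary endpoint differently, as the "amount of morphine equivalent administered intra-operative and during the first 24 hours after procedure". It reports the endpoint as a median with inter-quartile range and tests it with the Wilcoxon rank sum test.

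The paragraph just before Primary outcome makes "oral oxycodone available as needed for moderate breakthrough pain and IV morphine for severe pain". Fentanyl appears in the formula but is not among these rescue drugs.

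**The concern.** A composite opioid score is only as good as its weights. The fentanyl dose is entered in mcg and the other two IV drugs in mg. That is legitimate, because each unit is printed, but it hides the implied potency ratios. On a common unit, fentanyl sits close to hydromorphone and only tenfold above morphine, which looks low.

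The fentanyl factor is not a harmless change of scale. It weights one drug against the others, so it alters both the reported medians and the order of patients, and the rank sum test uses only that order. The arms also differ in timing: under Research Design and Procedures, the block follows induction and the infiltration comes at wound closure. Opioid given during surgery is therefore a plausible place for a difference, and on the Statistical Analysis definition it counts. With 12 patients per group, a few changes of rank can matter.

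**Working it through.** **Inputs from the Primary outcome paragraph:** IV fentanyl 0.03 per mcg, IV hydromorphone 20 per mg, IV morphine 3 per mg, oxycodone 1 per 5 mg tablet equivalent as written.

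**Input assumed, not in the documents:** IV fentanyl is 50 to 100 times as potent as IV morphine by weight.

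**1. Implied ratios.**
- Fentanyl: 0.03 × 1000 = 30 per mg.
- Fentanyl to IV morphine: 30 / 3 = 10.
- Fentanyl to hydromorphone: 30 / 20 = 1.5.
- Hydromorphone to IV morphine: 20 / 3 = 6.7.
- 100 mcg fentanyl: 100 × 0.03 = 3 MME, and 3 / 3 = 1 mg IV morphine.

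**2. Factor needed under the assumption.** Factor per mcg = potency ratio × 3 / 1000.
- At 50: 0.15. At 100: 0.30.
- Shortfall: 0.15 / 0.03 = 5 and 0.30 / 0.03 = 10.
- Each 100 mcg is then scored 15 − 3 = 12 to 30 − 3 = 27 MME too low.

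**3. Change of rank.** Child A receives 100 mcg of IV fentanyl; child B receives 2 mg of IV morphine (2 × 3 = 6).

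| Factor per mcg | A | B | Higher score |
|---|---|---|---|
| 0.03 | 3 | 6 | B |
| 0.15 | 15 | 6 | A |
| 0.30 | 30 | 6 | A |

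The order turns at 6 / 100 = 0.06 per mcg, which is below the whole assumed range.

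**4. Fentanyl's share of a total.** For an assumed 90 mcg of fentanyl with 3 mg of IV morphine:
- at 0.03: 2.7 / (2.7 + 9) = 23%
- at 0.15: 13.5 / 22.5 = 60%
- at 0.30: 27 / 36 = 75%

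**5. The plan's stated power.** The paragraph after Statistical Analysis gives 94% for 12 per group, effect size 1.5 and a two-sided 5% t test. With 22 degrees of freedom and noncentrality 1.5 × √6 = 3.67, the noncentral t gives 93.9%, so the figure reproduces. It uses a standardised effect and no MME mean or SD, so the conversion factor cannot change it.

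**6. Direction of any effect on the test.** Simulated two-sided 5% Wilcoxon test, 12 per arm, lognormal doses, CV 50% for fentanyl and 80% for IV morphine, no oxycodone. All doses are assumed. Repeat runs agree to within a point or two.

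| What the block spares | 0.03 | 0.15 | 0.30 |
|---|---|---|---|
| Fentanyl only (mean 90 vs 45 mcg; morphine 3 mg in both arms) | 9% | 50% | 74% |
| IV morphine only (mean 3 vs 1.5 mg; fentanyl 90 mcg in both arms) | 51% | 21% | 11% |
| Both halved | 84% | 97% | 97% |

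The printed factor costs power when the saving is in fentanyl and gains power when it is in morphine. If no fentanyl enters the endpoint, the factor has no effect.

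**The case against.** The strongest objection is that nothing in the documents contradicts 0.03. There is one fentanyl weight, no potency ratio and no conversion table, so the case rests on an outside assumption. That stands as a limit on what can be claimed. It does not remove the point: the implied 10:1 ratio is plain arithmetic, the plan gives no source that supports it, and no value in the assumed range is compatible with 0.03 beside x3 for IV morphine.

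A reader might infer more than the documents support:

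- **That 0.03 is a decimal slip.** A one-place shift gives 0.30, only the top of the range; 0.15 is not a decimal shift of 0.03. The cause is unknown.
- **That fentanyl all but drops out of the score.** In the example above it still supplies 23% of the total. Across other assumed mixes that include two oxycodone tablets, the share at 0.03 ran from about 5% (25 mcg with 4 mg IV morphine) to 60% (100 mcg with no morphine).
- **That the factor biases the comparison toward no difference.** The simulation reverses when the saving falls on morphine, and the plan does not say which opioid the block should spare.

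It is also fair to say that the impact depends on the endpoint window. If only the 48 hours after the procedure count, and rescue is with the named drugs, little fentanyl may enter. That makes the window a matter to settle alongside the weights; it does not justify an unsourced weight.

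**Conclusion.** The point holds as a scoring fault, conditional on one stated assumption. If IV fentanyl is 50 to 100 times as potent as IV morphine by weight, the formula under-weights it 5- to 10-fold relative to its own morphine term. Every total that contains IV fentanyl is then too low, by 12 to 27 MME per 100 mcg, and patients can be placed in the wrong order for the primary test.

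How much this changes the trial's result cannot be determined from the documents. It depends on how much fentanyl is given, which opioid the block spares, and which of the two endpoint windows applies; it is likely to be small if only post-procedure opioid is counted. The power percentages illustrate direction under assumed doses and do not forecast this trial. The sample-size statement is not affected.

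The factor should be settled before any data are scored, because it sits in the only definition of the primary endpoint and a change made after seeing results would be hard to defend.

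**What to change.** Before scoring:

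1. Take all conversion weights from one cited equianalgesic table with a common reference. Since IV morphine carries x3, the reference appears to be oral morphine; say so. Correct the fentanyl factor to that table and state the mcg-to-mg conversion.
2. Give the oxycodone term an explicit weight from the same table. At present a tablet count is added to milligram equivalents, so correcting fentanyl alone would leave the scale inconsistent.
3. Reconcile the two endpoint windows: 48 hours after the procedure, or intra-operative plus the first 24 hours.
4. Record raw doses by drug in the electronic data. The Ethics section has the data sheets destroyed after transfer, so a score stored only as a total could not be recomputed.
5. Report the primary comparison as a sensitivity analysis with the fentanyl factor varied over 0.15 to 0.30 per mcg.

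The weights serve to score the endpoint only and are not guidance for prescribing. The cost is a short edit to the endpoint definition, by-drug dose fields in the dataset and one added analysis. No extra patients or assessments are needed.

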The study has obtained departmental IRB approval and is seeking institutional IRB approval. Given very positive results from the adult population, we believe delaying this study will deprive large groups of children at other institutions from receiving a pain management technique that will improve their comfort and decrease the amount of narcotic needed.

The consent and assent will be explained to family and patient and alternatives which include no randomization will be offered.

A linking log will be used to deidentify data and a data sheet have been attached for review. The data sheets will be securely destroyed as soon as deidentified data is transferred to a electronic form on a secure server. The linking log will be stored in a locked cabinets within a locked office at the medical school.

Any complications will be reviewed quarterly with the EP cardiology/anesthesiology group and will be referred for departmental quality review if there is an increase in the number of complications compared to current base line when both the pain management injections are currently performed as standard of care.

References

1. Miller, Marc ; Garg, Jalaj ; Salter, Benjamin ; Brouwer, Thomas ; Mittnacht, Alex ; Montgomery, Morgan ; Honikman, Rafael ; Arkonac, Derya ; Choudry, Subbarao ; Dukkipati, Srinivas ; Reddy, Vivek ; Weiner, Menachem. Feasibility of subcutaneous implantable cardioverter-defibrillator implantation with opioid sparing truncal plane blocks and deep sedation. *Journal of Cardiovascular Electrophysiology*, Jan 2019, Vol.30(1), p.141
2. (Bashandy, GM and Abbas, DN. Pectoral nerves I and II blocks in multimodal analgesia for breast cancer surgery: a randomized clinical trial. *Reg Anesth Pain Med*. 2015; 40: 68–74;
4. Raza, Syed M. ; Vasireddy, Appa Rao ; Candido, Kenneth D. ; Winnie, Alon P. ; Masters, Robert W. A complete regional anesthesia technique for cardiac pacemaker insertion. *Journal of Cardiothoracic and Vascular Anesthesia*, 1991, Vol.5(1), pp.54-56

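### The primary-endpoint formula gives an MME factor for every IV opioid but none for oral oxycodone; taken literally, a 5 mg tablet scores 1 MME and patients can be ranked in the wrong order

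*Combined protocol and SAP*

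**What the plan says.** The Primary outcome section compares the groups on "total narcotic dose in milligram morphine equivalents (MME) needed for 48 hours after procedure". The sum begins "intravenous fentanyl (mcg) x0.03+intravenous hydromorphone (mg)x20" and continues "intravenous morphine(mg)x3+[number of oral oxycodone 5 mg/acetaminophen 325 mg tabs equivalents". Each of the three IV drugs is therefore a dose multiplied by a number. The oral oxycodone term is a number of tablet equivalents multiplied by nothing, and no other section supplies a factor.

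The paragraph just before it sets out the analgesic protocol: "Both groups of patients will also have oral oxycodone available as needed for moderate breakthrough pain and IV morphine for severe pain". The Statistical Analysis section then states: "Comparison between two groups will be evaluated by Wilcoxon rank sum test". The Ethics section adds, on record keeping: "The data sheets will be securely destroyed as soon as deidentified data is transferred to a electronic form on a secure server".

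**The concern.** A sum in MME is meaningful only if every term is on the MME scale. Here three terms are, and the fourth is a count. There are two ways to read it, and neither works:

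- **Literal.** Each 5 mg tablet adds 1, which is 0.2 MME per mg of oxycodone. Oral opioid is then heavily discounted against IV opioid.
- **A multiplier was dropped, or the word for equivalents stands for an unstated conversion.** The formula is then incomplete, and someone must choose the constant later, possibly with the data in view.

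Oxycodone and IV morphine are both on offer in both groups, for different pain severities, so mixed use is foreseeable. If the block changes how severe the pain is, the groups could differ in precisely the oral/IV mix. That is an inference from the plan's analgesic steps, not a documented rate. A rank test is unaffected by rescaling the whole sum, but it is affected by misweighting one component. With 12 patients per group, a few swapped ranks can matter.

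**Working it through.** **The plan's own figure.** The sample-size paragraph states 94% power for a two-sided 5% two-sample t test, 12 per group, effect size 1.5. With 22 degrees of freedom and noncentrality 1.5 × √(12/2) = 3.67, the power is 93.9%, so the figure reproduces. It rests on a standardized effect size and takes nothing from the MME formula, so it is unaffected by what follows.

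**Inputs from the Primary outcome section.** Fentanyl 0.03 per mcg; hydromorphone 20 per mg; IV morphine 3 per mg; oxycodone a count of 5 mg tablet equivalents, no factor.

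**Assumption.** The documents give no oxycodone factor. Let it be *f* MME per mg, so a tablet is worth 5*f*. I use *f* = 1 to 2, that is 5 to 10 MME per tablet.

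**What the literal formula implies.** One tablet = 1 MME = 1/3 = 0.33 mg IV morphine = 1/0.03 = 33 mcg IV fentanyl. At 5 to 10 MME per tablet it would equal 5/3 = 1.67 to 10/3 = 3.33 mg IV morphine. The literal weight is thus 5 to 10 times too small under the assumption.

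**When two patients change places.** Suppose one patient has *T* more tablets and the other has *M* mg more IV morphine. As written, the second ranks higher when 3*M* > *T*. With factor *f*, the first ranks higher when 5*fT* > 3*M*. The order reverses when

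*T* < 3*M* < 5*fT*, i.e. 1/3 < *M*/*T* < 5*f*/3.

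| *f* (MME per mg) | *M*/*T* (mg per tablet) | *M* for *T* = 4 (mg) |
|---|---|---|
| 1 | 0.33 to 1.67 | 1.3 to 6.7 |
| 1.5 | 0.33 to 2.50 | 1.3 to 10.0 |
| 2 | 0.33 to 3.33 | 1.3 to 13.3 |

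**Mixed-use example.** Patient A: 4 tablets + 1 mg IV morphine. Patient B: 1 tablet + 3 mg.

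| MME per tablet | A | B |
|---|---|---|
| 1 (literal) | 4 + 3 = 7 | 1 + 9 = 10 |
| 5 | 20 + 3 = 23 | 5 + 9 = 14 |
| 7.5 | 30 + 3 = 33 | 7.5 + 9 = 16.5 |
| 10 | 40 + 3 = 43 | 10 + 9 = 19 |

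**Break-even.** For 4 tablets (20 mg) against 2 mg IV morphine, the literal scores are 4 and 6. They tie at 6/20 = 0.3 MME per mg (1.5 per tablet), and any larger factor reverses them. The reversal does not need a factor near the top of the assumed range.

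**Can it reach the group comparison?** An invented data set, built so that the LA group uses more IV morphine and the block group more tablets, shows that it can. It is not trial data.

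- LA, IV morphine mg: 0, 1, 1, 2, 2, 2, 3, 3, 4, 4, 5, 6; tablets in the same order: 1, 0, 1, 1, 0, 2, 1, 0, 1, 2, 1, 0.
- Block, IV morphine mg: 0, 0, 0, 0, 1, 1, 1, 0, 2, 1, 2, 3; tablets: 1, 2, 3, 2, 3, 2, 4, 5, 3, 4, 4, 3.

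| MME per tablet | Median LA | Median block | Wilcoxon p |
|---|---|---|---|
| 1 (literal) | 8.5 | 5.5 | 0.12 |
| 5 | 12.5 | 19.5 | 0.060 |
| 7.5 | 15.0 | 27.0 | 0.013 |
| 10 | 17.0 | 34.5 | 0.003 |

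The weight alone turns a lower median in the block group into a higher one.

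**The case against.** The strongest reply is that this is an omitted constant, not a wrong sum. Inside a formula stated to be in MME, the bracketed term can be read as the morphine equivalents of the tablets, with the number left out. On that reading nothing is miscalculated, and the 5-to-10-fold error does not arise. That reading is fair, but the endpoint still cannot be computed from the plan, and the remedy is the same.

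Three further points stand as limits:

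- The range of 1 to 2 MME per mg comes from outside the documents, and the examples were chosen to show reversal. Pairs who use only one route, or in which one patient is at least as high on both, keep their order.
- The oral share is not given and also depends on the analysis window. Primary outcome uses 48 hours after the procedure, while Statistical Analysis uses intra-operative opioid plus the first 24 hours. That conflict is a separate matter, but it must be settled before the influence of the tablet weight can be judged.
- Nothing says that only a computed total goes into the electronic file, and the data sheet is not in the text available. The risk that the weighting could not be corrected after the sheets are destroyed is therefore conditional.

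None of these supplies the missing factor.

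**Conclusion.** The point holds and must be fixed before analysis. As written, the formula either scores a 5 mg oxycodone tablet at 1 MME, making three tablets equal to 1 mg of IV morphine, or leaves the primary endpoint undefined. If oxycodone is worth 1 to 2 MME per mg, the literal weight is too small by a factor of 5 to 10. Two patients then swap order whenever the IV morphine difference is between 0.33 and 1.67 mg (at 1 MME per mg), or 0.33 and 3.33 mg (at 2), per tablet of opposite difference.

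The size and direction of any effect on the group comparison cannot be derived from the documents. There is no effect on the ranks if patients use only tablets, and none on the stated power. Confidence is high that the factor is absent and that the order can change; how much this would alter the trial's result is unknown.

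**What to change.** Before any outcome data are analyzed, replace the last term with oral oxycodone in mg multiplied by an explicit factor. Take that factor from one cited equianalgesic table, on the same scale as the three IV factors.

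Before the data sheets are destroyed, make sure the electronic file holds each opioid's dose as its own field (mg, or mcg for fentanyl) and not only the MME total. The endpoint can then be recomputed if the weighting is questioned.

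The cost is one line in the formula and one dose field per opioid. No patients are added and no treatment changes. If the data sheet already records doses by drug, the second step only requires carrying those fields across.

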**Truncal ultrasound guided regional anesthesia for implantation and revision of
AICDs and pacemakers in pediatric patients**

NCT04184349

Version Date: 12/19/2019

Title: Truncal ultrasound guided regional anesthesia for implantation and revision of AICDs and pacemakers in pediatric patients.

PI: [name] (Anesthesiologist)

Co PIs: [name] (Electrophysiologist), [name] (Electrophysiologist), [name] (Anesthesiologist), [name] (Anesthesiologist), [name] (Anesthesiologist), [name] (Anesthesiologist)

Population: Children undergoing pacemaker and/or Automatic Implantable Cardioverter Defibrillator implantation at Children's Memorial Hermann Hospital

Study Duration: Data will be collected from procedure for 48 hours

Purpose

The purpose of this study is to determine the efficacy and safety of truncal blocks for pacemaker and Automatic Implantable Cardioverter Defibrillator implantation in children

Hypothesis Truncal block is effective, safe and feasible for implantation of AICDs and pacemakers in children.

Research Design and Procedures to be Used

Written consent for the study will be obtained from a parent. We will also obtain consent from the patient if they are older than 10 years together with their parents.

The patients will be simply randomized by a pre-determined computer generated random numbers and allocated to one of two groups. The group allocation (LA group or B group) will be concealed in sealed opaque envelopes that will be opened after enrollment of the patients. In one group (the LA group), only the local anesthetic infiltration will be performed. In the block group (the B group), PECS and TTP blocks will be performed. The ultrasound-guided nerve blocks will be performed by the anesthesiologist after induction of anesthesia and endotracheal intubation. The left upper extremity angiogram will be performed prior to block to ensure the correct side for the implant. The local anesthetic group will have wound infiltration as routine care by the electrophysiologist at the time of wound closure. Both of these blocks have been used successfully in our institution and the purpose of the study is to prospectively evaluate whether there is a decrease in amount of narcotic medications need and track complications. There is no deviation from the standard of care as currently practiced.

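### The primary total is defined over 48 hours and most children are expected home before then, but the public text gives no way to record opioid taken after discharge and no rule for scoring early discharge; the analysis section names a different window.

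*Combined protocol and SAP*

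**What the plan says.** The Primary outcome section compares the groups on "total narcotic dose in milligram morphine equivalents (MME) needed for 48 hours after procedure". Part of its reason for choosing 48 hours is that "most patients would be discharged prior to the 48 hour mark". Study Duration agrees on the length: "Data will be collected from procedure for 48 hours".

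The Statistical Analysis section describes the primary endpoint differently, as the "amount of morphine equivalent administered intra-operative and during the first 24 hours after procedure". This is the definition followed by the Wilcoxon rank sum test.

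On the opioids themselves, "Both groups of patients will also have oral oxycodone available as needed for moderate breakthrough pain and IV morphine for severe pain". The morphine-equivalent formula has three intravenous terms and one oral term, the "number of oral oxycodone 5 mg/acetaminophen 325 mg tabs equivalents". It does not say whether tablets taken at home count. The Ethics section says that "a data sheet have been attached for review", but the sheet is not part of the public document.

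No section describes a diary, call, visit, tablet count or prescription record after discharge. None says whether the hours after an early discharge are scored as zero, treated as missing or extrapolated.

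**The concern.** By the plan's own expectation, most children spend the end of the 48-hour window at home. If the total is built from hospital records, a child who leaves at 24 hours contributes 24 hours of use and a child who stays to 48 hours contributes 48. The recorded quantity is then need multiplied by the share of need that falls before discharge.

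That matters most if stay differs between groups. The Risks and Potential Benefits section expects the block to improve analgesia and reduce opioid side effects, and either could plausibly bring discharge forward. With 12 per group, stay could also differ by chance. If block patients left earlier, their recorded opioid would be lower even with identical need. If they left later, a real saving would be partly hidden.

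The side-effect outcomes are also to be tracked for 48 hours and share the gap, though less seriously, because the plan expects them early.

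**Working it through.** **1. The plan's own figure.** The sample-size paragraph gives 94% power for 12 per group, effect size 1.5 and a 5% two-sided t test. The noncentrality is 1.5 × √(12/2) = 3.674 on 22 degrees of freedom, which gives 93.9%. The figure reproduces. It assumes that the endpoint is fully observed, so it does not bear on this point.

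**2. The two definitions side by side.**

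| | Primary outcome | Statistical Analysis |
|---|---|---|
| Start | after the procedure | intra-operative |
| End | 48 h | 24 h |
| Who loses data if only hospital use is recorded | anyone discharged before 48 h (most, by the plan's expectation) | only those discharged before 24 h |

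**3. Share of 48-hour use recorded by discharge at time L.** With even accrual the share is L/48. With use declining at half-life h it is (1 − 0.5^(L/h)) / (1 − 0.5^(48/h)). The documents give neither L nor h, so both are assumptions.

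| Discharge | Even | h = 24 h | h = 12 h | h = 6 h |
|---|---|---|---|---|
| 24 h | 50% | 67% | 80% | 94% |
| 36 h | 75% | 86% | 93% | 99% |

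**4. Effect on the comparison when there is no true effect.** From the plan: 12 per group and a two-sided 5% Wilcoxon test. Assumed: lognormal 48-hour need with log-SD 0.5 to 0.8; mean LA stay 36 h, SD 6 h; group B leaving 6 or 12 h earlier; only in-hospital use recorded. There were 6,000 simulated trials per setting. Within each range of false-positive rates, the higher rate generally belongs to log-SD 0.5.

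| Use over time | 6 h earlier: B total lower by | False positives | 12 h earlier: B total lower by | False positives |
|---|---|---|---|---|
| Even | 17% | 7–12% | 33% | 20–40% |
| h = 24 h | 10% | 5–7% | 23% | 11–21% |
| h = 12 h | 7% | 5–6% | 15% | 7–11% |
| h = 6 h | 2% | 4–5% | 6% | about 5% |

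Hand check of the even row: mean shares are 36/48 = 0.75, 30/48 = 0.625 and 24/48 = 0.50. The ratios 0.625/0.75 = 0.83 and 0.50/0.75 = 0.67 match the 17% and 33% reductions.

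With equal stays the false-positive rate is about 4–5% under every pattern.

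**5. The same scenario with a 24-hour post-procedure window and even accrual.** Group B's total is about 2% lower for the 6 h gap and 10% lower for the 12 h gap. False positives are about 4–7% across the two.

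**6. Effect on power.** These runs assume a true effect of 1.5 SD on the log scale (log-SD 0.6), again with the 48-hour total. Wilcoxon power with full capture is about 92%. With equal mean stays of 30 h it is 89–91%. If the block group stays longer (36 h against 24 h), it falls to about 76% (h = 12 h) or 38% (even accrual).

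**The case against.** The strongest reply is that the only endpoint definition tied to a test is the 24-hour one. A reader might infer that children with 24 and 48 hours of observation will be compared as if both had 48-hour totals. The documents do not establish that, because the analysis text uses 24 hours, where the loss is small. This stands. It does not remove the point, since the Primary outcome section and Study Duration both say 48 hours.

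A reader might also infer that nothing at all captures home opioid. That goes beyond the evidence: the data sheet is not shown, data are said to be collected for 48 hours, and the tablet term does not exclude home tablets. What can be said is that the public text does not describe how.

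Next, even accrual is the unfavorable case. As-needed opioid on top of scheduled non-opioid analgesics could well decline over time, and the distortion then shrinks sharply. Nor is all late need lost. The plan states that "the local anesthetic duration for either local infiltration or block is 6-12 hours", and need at 12–24 hours is still recorded in hospital for a child who stays at least 24 hours.

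Finally, no section gives discharge times, discharge criteria or a link between allocation and stay. The 6 and 12 hour gaps are assumptions, and with equal stays there is no inflation. All of this stands as a limit on the size.

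**Conclusion.** The concern holds in a limited form. Under the 48-hour definition, the public text leaves open both how opioid use after discharge is recorded and how early discharge is scored, although most children are expected to leave within the window. If only in-hospital use is recorded, the total partly reflects length of stay. The two primary windows also conflict and must be reconciled; under the 24-hour definition the problem is confined to children discharged before 24 hours.

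For the 48-hour total with no true effect, the illustrative false-positive rate is about 4–12% for a 6-hour difference in stay and 5–40% for 12 hours. The lower ends correspond to use declining with a 6-hour half-life, the upper ends to even accrual. These figures rest on assumed stays, gaps and accrual. The documents do not support reading the 40% as an expected error rate, or concluding that the result will favor the block: the direction depends on which group stays longer, and equal stays give about 4–5%.

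The change is worth making before enrollment, because home use not recorded at the time cannot be reliably recovered later.

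**What to change.** State one primary window, including whether intra-operative opioid counts, and use it in both the Primary outcome and Statistical Analysis sections.

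- **If the window is 48 hours:** add one scheduled contact with the family at 48 hours. Record opioid tablets taken since discharge, with a tablet count, and add them to the oral term already in the formula. Ask about side effects on the same call. Record discharge time, report length of stay by group, and state how a child is scored if the contact fails.
- **Otherwise:** make the primary window one that patients complete in hospital under existing practice, and report 48 hours as secondary.

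If the unpublished data sheet already captures home use, a sentence saying so, together with the scoring rule, would close the capture gap; the two windows would still need reconciling.

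The cost is about 24 calls (2 × 12 patients) and an added discharge-time field on the data sheet. The drawback is that home use would be parent-reported. The change concerns recording only and alters no treatment or discharge decision.
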